Company:	Sanofi Pasteur
Investigational Product:	SP0202 - 21-valent pneumococcal conjugate vaccine
Active Substances:	Streptococcus pneumoniae serotypes 1, 3, 4, 5, 6A, 6B, 7F, 8, 9N, 9V, 10A, 11A, 12F, 14, 15B, 18C, 19A, 19F, 22F, 23F, and 33F

Title of the Study:	Safety and Immunogenicity of a Pneumococcal Conjugate Vaccine (PCV) when Administered Concomitantly with Routine Pediatric Vaccines in Healthy Toddlers and Infants
Development Phase:	Phase II
Coordinating Investigator (Stage I):	
Coordinating Investigator (Stage II):	
Study Sites:	This will be a multi-center study conducted at approximately 42 sites in the United States (US), 8 sites in Canada and 2 sites in Honduras Investigators and sites will be listed in the “List of Investigators and Centers Involved in the Trial” document.
Planned Study Period:	Quarter 2 of 2020 (first visit of the first subject) to Quarter 2 of 2023 (last contact of the last subject)
Study Design, Schedule of Study Procedures, and Methodology:	
This will be a Phase II, randomized, active-controlled, observer-blind (double-blind across investigational vaccine formulations), age de-escalating, multi-centered study to assess the safety and the immunogenicity of 3 different formulations of an investigational pneumococcal conjugate vaccine (PCV) in approximately 140 healthy toddlers (12–15 months of age [MoA]), and 700 healthy infants (aged 42 to 89 days). The vaccine is referred to as SP0202 in what follows.
 
The study will involve 2 stages:
 
 • In Stage I, toddlers aged between 12 and 15 months, who previously received the 3-dose primary series of Prevnar®13, will receive 1 dose of either one SP0202 formulation (Group 1, 2, and 3) or Prevnar 13 (Group 4), concomitantly administered with Pentacel® • In Stage II, infants aged 2 months will receive 3 doses of either one SP0202 formulation or Prevnar 13 approximately at 2, 4, and 6 MoA and a 4th dose at 12 to 15 MoA (Groups 5, 6, 7, and 8), co-administered with pediatric vaccines recommended at this age 
All infants will receive the following routine vaccines (summarized in Table 1):
 
 • Pentacel (DTaP-IPV/Hib) at 2, 4, 6 months of age* • RotaTeq® (pentavalent rotavirus vaccine [RV5]) at 2, 4, and 6 months of age • M-M-R® II (measles, mumps, rubella [MMR] vaccine) at 12 to 15 months of age • VARIVAX® (varicella vaccine) at 12 to 15 months of age

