6.5 Randomization and Allocation Procedures

On the day of enrollment, subjects who meet the inclusion/exclusion criteria and sign the ICF will be randomly assigned to Groups 1 through 4 in a 1:1:1:1 ratio to have approximatively 140 subjects (35 subjects in each treatment group) for toddlers subjects (Stage I) or to Group 5 through 8 in a 1:1:1:1 ratio to have approximatively 700 subjects (175 subjects in each treatment group) for infants subjects (Stage II). Stage II randomization will be at least stratified by country.

Following DMC assessment, in case one or more of the SP0202 formulations may not be included in the stage II, the randomization list will match with the selected groups for stage II; the sample size of each group will remain unchanged (175 subjects by group) and the ratio between groups will be balanced.

Site staff will connect to the IRT, enter the identification and security information, and confirm a minimal amount of data in response to IRT prompts. The IRT will randomize the subjects and then provide the vaccine assignment and have the site staff confirm it. The full detailed procedures for group allocation are described in the Operating Guidelines. If the subject is not eligible to participate in the study, then the information will only be recorded on the subject recruitment log.

IRT will also be used to randomly allocate subject to the OPA subset in Stage II (around 125 infants by group). This allocation has no impact on the study conduct on site; the list of selected subjects will be communicated to the laboratory personnel.

Subject numbers that are assigned by the IRT will consist of a 12-digit string (a 3-digit country identifier, a 4-digit study center identifier, and a 5-digit subject identifier). The first digit of the subject identifier will be '1' for toddlers subjects randomized into Stage 1 and '2' for infants subjects randomized into Stage 2. For example, Subject 840000110005 is the fifth toddler subject enrolled in Center Number 1 in the US in stage I (840 being the US country code), and Subject 840000120005 is the fifth infant subject enrolled in Center Number 1 in the US (840 being the US country code).

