12.1.1 Hypotheses and Statistical Methods for Primary Objective(s)

12.1.1.1 Hypotheses

All analyses will be descriptive; no hypothesis will be tested.

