**Table 5.1: Descriptive statistics produced**

Baseline characteristics and follow-up description	Categorical data	Number of participants. Percentage of participants.
	Continuous data	Mean, standard deviation, quartiles, minimum, and maximum.
Clinical safety results	Categorical data	Solicited: Number and percentage (95% CIs) of participants. Unsolicited: Number and percentage (95% CIs) of participants, and number of events.
Immunogenicity results	Categorical data (seroprotection, cutoff, thresholds)	Number and percentage (95% CIs) of participants.
	Continuous data (titer / data)	Log10: Mean and standard deviation. Anti-Log10 (work on Log10 distribution, and anti-Log10 applied): Geometric mean, 95% CI of the geometric mean, quartiles, minimum, and maximum. Graphical representation by Reverse Cumulative Distribution Curve (RCDC). Boxplots and Forest plots.

The CI for the single proportion will be calculated using the exact binomial method (Clopper-Pearson method, quoted by Newcombe (2)), ie, using the inverse of the beta integral with SAS®.

For immunogenicity results, assuming that Log10 transformation of the titers / concentrations follows a normal distribution, at first, the mean and the 95% CI will be calculated on Log10 (titers / data) using the usual calculation for normal distribution (using Student's t distribution with n-1 degree of freedom), then antilog transformations will be applied to the results of calculations, in order to provide geometric means (GMs) and their 95% CI.

CIs of the difference of proportions between 2 groups will be computed using the Wilson Score method without continuity correction. CIs of ratio of GMTs / GMCs between 2 groups will be computed from the difference in means of log10 transformed titers/concentrations between 2 groups with normal approximation.

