#### *Immunogenicity - Stage II infants*

The point estimates and their 95% CI of the following parameters will be presented for each group for each pneumococcal serotype specific IgG concentrations when applicable:

- Percentage of participants with a PD3 and PD4 serotype specific IgG concentrations  $\geq 0.35 \mu\text{g/mL}$
- GM of serotype specific IgG concentrations / titers (pre-dose 1\* as applicable, PD3, pre-dose 4, PD4)

- GM of serotype specific IgG concentrations / titers ratio (PD3/pre-dose 1\* as applicable, PD4/pre-dose 4)

In addition, difference between any SP0202 group (Group 5 to 7) and the Prevnar 13 group (Group 8) and between SP0202 groups will be presented in terms of:

- Differences of percentages of participants with serotype specific IgG concentration  $\geq 0.35 \mu\text{g/mL}$  and 95% CI at PD3
- GM ratio of serotype specific IgG concentrations between groups and 95% CI at PD3 and PD4

Several graphical representations will be used such as: RCDCs of individual concentrations, Boxplots of the  $\log_{10}$  concentrations and Forest plots of GMCs for all serotypes.

\*Pre-dose 1 BL is done only for participants enrolled before protocol amendment V5.0

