##### **5.1.2.2.2 Stage II infants**

###### ***Immunogenicity of SP0202 or Prevnar 13***

The point estimates and their 95% CI of the following parameters will be presented for each group in the OPA subset and for each pneumococcal serotype specific OPA titers:

- Percentage of participants with a PD3 and PD4 serotype specific titer above or equal to LLOQ
- GM of serotype specific titers (PD3, pre-dose 4, PD4)
- GM of serotype specific titers ratio (PD4/pre-dose 4)

In addition, the difference between any SP0202 group (Group 5 to 7) and the Prevnar 13 group (Group 8) and between SP0202 groups will be presented in terms of:

- GM ratio between groups and 95% CI at PD3 and PD4

Several graphical representations will be used such as: RCDCs of individual concentrations and Forest plots of GMCs for all serotypes.

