#### ***Subgroup Immunogenicity analyses***

For Infant participants, exploratory analyses will be done according to Gender (two categories: Male, Female) and Race (two categories: the modality(ies) the most represented versus the pool of the other modalities) on the main parameters:

- Percentage of participants with a PD3 serotype specific IgG concentrations  $\geq$  0.35  $\mu$ g/mL
- GM of serotype specific IgG concentrations (PD3, pre-dose 4, PD4)
- GM of serotype specific ratio concentrations (PD4/pre-dose 4)

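### Stage II is randomized by country, but the IgG and OPA ratios ignore country, so their 95% intervals are slightly too wide if countries differ

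*SAP*

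**What the plan says.** Protocol 6.5 states that "Stage II randomization will be at least stratified by country", which leaves open whether other factors were added. The Study Sites entry of the protocol synopsis lists "approximately 42 sites in the United States (US), 8 sites in Canada and 2 sites in Honduras". Infants per country are not given.

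The method for between-group ratios stands in SAP section 5, after Table 5.1, and in the same words in Protocol 12.1.1.2: "CIs of ratio of GMTs / GMCs between 2 groups will be computed from the difference in means of log10 transformed titers/concentrations", with a normal approximation. It is a plain two-group comparison. SAP 5.1.1.2 applies it to Stage II IgG ("GM ratio of serotype specific IgG concentrations between groups and 95% CI at PD3 and PD4"), and SAP 5.1.2.2.2 applies it to OPA ("GM ratio between groups and 95% CI at PD3 and PD4"). Tables 5.2 and 5.3 list the same comparisons, each SP0202 group against Prevnar 13 and the SP0202 groups against each other, with no covariate.

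The SAP names no stratification factor. In SAP 5.1.3, "exploratory analyses will be done according to Gender (two categories: Male, Female) and Race"; country is not included. Country enters the analysis text only as a reason why the number of hepatitis B doses will vary.

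For OPA, Protocol 6.5 says "IRT will also be used to randomly allocate subject to the OPA subset in Stage II (around 125 infants by group"). It does not say whether that draw is stratified by country. Protocol 12.1.1.1 states "All analyses will be descriptive; no hypothesis will be tested".

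**The concern.** Stratifying by country makes the arms nearly equal in country mix, so a difference in level between countries largely cancels in the comparison of arms. A two-sample standard error does not use that fact. It counts the between-country spread as noise, and the interval comes out wider than the design warrants. Chance country imbalance can also return through dropout, per-protocol exclusions and the OPA draw, and the unadjusted ratio leaves it uncorrected.

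What is at stake is precision only. Protocol 1.4 gives choosing a lead formulation for Phase III as a purpose of the work, and the intervals around the formulation ratios are what the trial offers for that choice. OPA has the fewest infants. The absence of country from the subgroup list does not affect interval width; it only shows that country is not used elsewhere in the pneumococcal analyses.

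**Working it through.** **Figures taken from the plan.** Stage II has 175 infants per group, allocated 1:1:1:1, with dropout of 20% at PD3 and 30% at PD4 (SAP 5.5). The plan's evaluable numbers reproduce: 35 × 0.9 = 31.5 (stated as 31), 175 × 0.8 = 140, and 175 × 0.7 = 122.5 (stated as 122). The same rates applied to the OPA subset give 125 × 0.8 = 100 at PD3 and 125 × 0.7 = 87.5, taken as 88, at PD4. The plan gives no interval width, SD or power to reproduce.

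**Assumptions, not in the documents.** Within-country SD of log10 IgG is 0.45. Two countries are alike and the third is shifted by δ. Country shares are 42/8/2 (as the sites), 60/25/15 or 50/10/40, with share p in the third country.

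**Formula.** Let W be the within-country variance and B = p(1 − p)δ² the between-country variance. With country balanced, the true variance of the difference uses W, while the unadjusted standard error uses W + B. The width ratio is therefore √(1 + B/W).

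**Fixed-balance result**, 140 per group, W = 0.45² = 0.2025, δ = log10(2) = 0.301, δ² = 0.0906. The adjusted 95% half-width is 1.96 × 0.45 × √(2/140) = 0.1054 log10, that is, the ratio times or divided by 10^0.1054 = 1.275.

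| Shares | p(1 − p) | B | B/W | Excess width | Unadjusted factor | Extra infants per group to compensate (140 × B/W) |
|---|---|---|---|---|---|---|
| 42/8/2 | 0.0370 | 0.0034 | 0.0166 | 0.82% | 1.277 | about 2 |
| 60/25/15 | 0.1275 | 0.0116 | 0.057 | 2.81% | 1.283 | about 8 |
| 50/10/40 | 0.2400 | 0.0217 | 0.107 | 5.23% | 1.291 | about 15 |

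**With random losses.** A simulation (6,000 runs per scenario, 175 per group, equal country counts in each arm) compared the unadjusted pooled t interval with least squares on group plus country. Attrition was random; for OPA, 125 of 175 per group were first drawn at random. Excess width of the unadjusted interval for IgG at PD3:

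| Shares | SD 0.45, 1.5-fold | SD 0.45, 2-fold | SD 0.35, 2-fold |
|---|---|---|---|
| 42/8/2 | 0.2% | 0.8% | 1.3% |
| 60/25/15 | 0.9% | 2.7% | 4.6% |
| 50/10/40 | 1.7% | 5.2% | 8.5% |

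With no country effect the figure is about −0.1%. For OPA (100 and 88 per group, SD 0.6, 2-fold) it is 0.2% to 2.8%. Unadjusted coverage at SD 0.45 was 94.7% to 96.1%.

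**Second calculation with other assumptions.** Here the SD is 0.5, the shifted country holds 5%, 15% or 35% of infants, and randomization uses permuted blocks of 4 within country. The same formula gives excess width of 0.1–0.5% at δ = 0.1, 0.4–1.8% at 0.2, 0.9–4.0% at 0.3 and 2.4–10.8% at 0.5 (about 3-fold).

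Losses return a share f = 1 − n/175 of the country imbalance, so true coverage is 2Φ(1.96 √[(W + B)/(W + fB)]) − 1. At 15% share, δ = 0.3 and n = 140: f = 0.20, W = 0.25, B = 0.1275 × 0.09 = 0.0115, and coverage is 95.4%. Across shares at δ = 0.3, coverage is 95.2–95.7% at PD3, 95.1–95.6% with 125 OPA infants and 95.1–95.6% with 122 at PD4. Simulation (4,000 runs per scenario) agreed within about 0.3 points. Country-adjusted coverage was 94.4% to 95.4%.

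**Proportions at or above 0.35 µg/mL.** A country-stratified Newcombe interval with Mantel-Haenszel weights was compared with the planned Wilson interval over 20,000 runs, with response 70–95% and country counts per group of 113/22/5, 84/35/21 and 70/14/56. Its width was 1.000 to 1.035 times the planned width, so stratifying gains nothing there.

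**The case against.** The strongest objection is that this is an optional efficiency gain. The only country information in the documents is the site count. On that basis the excess is 0.2–0.8% at SD 0.45, or 1.3% at SD 0.35 with a 2-fold shift. The larger figures need 15% or 40% of infants to come from a country that could hold as few as 2 of 52 sites. No passage reports a country effect on pneumococcal response, and the study vaccines follow one schedule everywhere. This stands as a limit on size. The documents do not fix enrollment, though, and Protocol 5.1.2 acknowledges that routine schedules differ between the countries.

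Second, the SAP's normal approximation may mean a z multiplier, while the comparison above uses t. A z interval is narrower than t by 0.44% at 140 per group, about 0.6% at 100 and 0.7% at 88. On that reading the smallest scenarios vanish or reverse: 0.2% becomes about −0.2%, and the 2-fold result at 42/8/2 falls to about +0.4%. The wording is ambiguous, and the larger scenarios are unaffected in direction.

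Third, once losses unbalance the countries, an adjusted ratio will generally not equal the quotient of the displayed group GMCs. Reporting the unadjusted ratio alongside answers this.

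Fourth, Protocol 6.5 refers detailed allocation procedures to the Operating Guidelines, which are not available here. Other strata, or stratification of the OPA draw, may be specified there. That is why the point is only that the protocol and SAP do not state them.

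**Conclusion.** The concern holds and is minor. The Stage II ratio analyses omit the factor that the randomization is stratified on. If countries differ, the intervals are slightly conservative. For a 2-fold difference in one country and SD 0.45, the excess is about 0.8% to 5.2%, and it is nearest the bottom of that range if enrollment follows the sites. Excess near 11% appears only with a roughly 3-fold shift in a country holding 35% of infants. Point estimates stay valid, and coverage is not materially below 95% in any scenario. Because the analyses are descriptive, without hypothesis or margin, no decision rule changes.

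The sizes rest on assumed SDs, shares and shifts, and on losses unrelated to group. The direction rests only on near-balance by country, which stratified allocation provides and random loss weakens but does not reverse.

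**What to change.** - State in the SAP which strata the IRT actually used for Stage II, and whether the OPA draw was stratified.
- For the Stage II IgG GMC and OPA GMT ratios at PD3 and PD4, fit a linear model of log10 value on group plus country (and any other stratum used). Back-transform the group differences with t-based 95% intervals, and keep the unadjusted ratio as supportive.
- Keep the planned Wilson interval as the main analysis of the difference in the percentage at or above 0.35 µg/mL. If a country-stratified difference is added, make it a sensitivity analysis with a rule, set in advance, for pooling sparse countries.

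The cost is SAP wording and one standard model, with no new data, visits or participants. If countries do not differ, the adjusted interval is wider by only about 0.1%.

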Statistical Methods:	
Statistical analyses will be performed on safety and immunogenicity data collected for each stage as follows:
 
• 1 unblinded analysis on immunogenicity and safety data collected in toddlers (Stage I) up to V02 and including 6-month follow-up data if available at the time of V01-V02 immunogenicity data release• 1 unblinded analysis on immunogenicity data (serotype specific IgG concentration) collected on the first 350 randomized infants (Stage II) up to 1 month after the third dose of PCV• 1 unblinded analysis on data collected in infants (Stage II) up to 1 month after the third dose of PCV and including Stage I data of the 6-month follow-up (if not done as part of first analysis). The analysis may be conducted in two steps depending on the duration of immunogenicity testing: 1 – an early analysis on safety and serotype specific IgG results (primary endpoints) of all subjects up to 1 month after the third dose; 2 – an analysis on all results (primary and secondary endpoints) up to 1 month after the third dose• 1 unblinded analysis on immunogenicity and safety collected in infants (Stage II) up to 1 month after the fourth dose of PCV. The 6-month safety follow-up data will be included, depending on the timing of this analysis.• 1 final analysis on complete Stage II data including the 6-month follow-up, if needed. 
Analyses
 
All analyses will be descriptive; no hypotheses will be tested.
 
The per-protocol population and the Full Analysis Set will be used for the immunogenicity analyses and the safety population will be used for the safety analyses.
 
For the main parameters, 95% confidence intervals (CIs) of point estimates will be calculated using the normal approximation for quantitative data and the exact binomial distribution (Clopper-Pearson method) for proportions.
 
CIs of the difference of proportions between 2 groups will be computed using the Wilson Score method without continuity correction.
 
CIs of ratio of geometric mean titers (GMTs) / GMCs between 2 groups will be computed from the difference in means of log10 transformed titers/concentrations between 2 groups with normal approximation.

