12.1 Statistical Methods

For immunogenicity data, assuming that log10 transformation of the titers / concentrations and titers / concentrations ratio follows a normal distribution, first, the mean and 95% confidence intervals (CIs) will be calculated on log10 (titers / concentrations; titers / concentrations ratio) using the usual calculation for normal distribution, then antilog transformations will be applied to the results of calculations, to compute geometric mean titers / concentrations (GMTs / GMCs) and geometric mean of the individual titer / concentration ratios (GMTRs / GMCRs) and their 95% CIs.

The 95% CIs of point estimates will be calculated using the exact binomial distribution (Clopper-Pearson method (43)) for proportions.

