#### *Immunogenicity - Stage I toddlers*

The point estimates and their 95% CI of the following parameters will be presented for each group before and 1-month post-vaccination for each pneumococcal serotype specific IgG concentrations:

- GM of serotype specific IgG concentrations
- GM of IgG concentrations ratio (post- / pre-vaccination)

In addition, the difference between any SP0202 group (Group 1 to 3) and the Prevnar 13 group (Group 4) will be presented in terms of:

- GM ratio of serotype specific IgG concentrations between groups (SP0202/Prevnar 13) and 95% CI at 1-month post-vaccination

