##### **5.1.2.2.1 Stage I toddlers**

###### ***Immunogenicity of SP0202 or Prevnar 13***

The point estimates and their 95% CI of the following parameters will be presented for each group before and 1-month post-vaccination for pneumococcal serotype specific OPA titers:

- GM of serotype specific titers, GM of titers ratio (post- / pre-vaccination)
- Percentage of participants with a serotype specific titer above or equal to LLOQ

In addition, the difference between any SP0202 group (Group 1 to 3) and the Prevnar 13 group (Group 4) will be presented in terms of:

- GM ratio between groups (SP0202/Prevnar 13) and 95% CI at 1-month post-vaccination

Several graphical representations will be used such as: RCDCs of individual concentrations and Forest plots of GMTs for all serotypes.

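### The SAP names no quantile, degrees of freedom or variance estimator for between-group GMC/GMT ratio CIs; read literally as z, the toddler intervals are about 2% too narrow on the log10 scale

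*SAP*

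**What the plan says.** SAP section 5, in the text below Table 5.1, gives two rules in neighbouring paragraphs.

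- **One group.** The CI of the mean log10 titer or concentration uses Student's "t distribution with n-1 degree of freedom" and is then back-transformed.
- **Two groups.** The CI of a GMT or GMC ratio comes from the difference in mean log10 values "between 2 groups with normal approximation". The SAP adds no quantile, degrees of freedom, or choice between pooled and unpooled variance.

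The Protocol words the ratio CI in the same way in its synopsis (Statistical Methods) and in section 12.1.1.2. For single groups it is less specific than the SAP. The synopsis says that CIs "will be calculated using the normal approximation for quantitative data and the exact binomial distribution (Clopper-Pearson method) for proportions". Section 12.1 says that they are obtained "using the usual calculation for normal distribution, then antilog transformations will be applied to the results of calculations". Neither names Student's t.

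The SAP plans toddler ratios of each SP0202 group to Prevnar 13 for IgG (section 5.1.1.2: "GM ratio of serotype specific IgG concentrations between groups (SP0202/Prevnar 13) and 95% CI at 1-month post-vaccination") and for OPA (section 5.1.2.2.1: "GM ratio between groups (SP0202/Prevnar 13) and 95% CI at 1-month post-vaccination"). It plans infant ratios at PD3 and PD4. SAP section 5.5 anticipates 31 evaluable toddlers per group, and 140 (PD3) and 122 (PD4) infants per group. No hypothesis is tested (SAP section 5.1.1).

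**The concern.** The variance is estimated from the data in both situations, so the reason for using Student's t in one group applies equally to a difference between two groups. The SAP added Student's t to the Protocol's single-group sentence and left the ratio sentence as it was. A programmer could reasonably take the two phrases as two different methods and use 1.96 for the ratios.

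With about 31 toddlers per group, a z interval labelled 95% covers a little less than 95%. The rule governs 21 serotypes × 3 comparisons × 2 assays = 126 Stage I ratio intervals, and under z the shortfall has the same direction in all of them. They would also stand beside single-group intervals built by a different method. Apart from calibration, two programmers could obtain different limits from the same data.

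Nothing is tested on these intervals. They will still be read, because Protocol section 1.4 describes the formulations as carried forward to identify a lead for Phase III.

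**Working it through.** **Inputs.** Enrolled per group: 35 toddlers and 175 infants. Drop-out: 10% in toddlers, 20% (PD3) and 30% (PD4) in infants. Evaluable per group: 31, 140 and 122 (all SAP section 5.5). Allocation is 1:1:1:1 (SAP section 3.1). The documents give no SD, CI width or coverage.

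**Step 1: reproduce the plan's own figures.** Evaluable n = N × (1 − d), rounded down:
- 35 × 0.90 = 31.5, giving 31
- 175 × 0.80 = 140
- 175 × 0.70 = 122.5, giving 122

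All three agree with the SAP.

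**Step 2: compare the quantiles.** With n per group and equal variances, df = 2n − 2. On the log10 scale the t interval is wider than the z interval by the factor t(0.975, df) / 1.9600, whatever the SD. Coverage of the z interval is 1 − 2·P(T_df > 1.96).

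| n per group | df | t | t / z | Coverage with z |
|---|---|---|---|---|
| 31 (toddlers, anticipated) | 60 | 2.0003 | 1.021 | 94.5% |
| 35 (toddlers, no loss) | 68 | 1.9955 | 1.018 | 94.6% |
| 122 (infants, PD4) | 242 | 1.9698 | 1.005 | 94.9% |
| 140 (infants, PD3) | 278 | 1.9685 | 1.004 | 94.9% |

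A simulation with normal data and equal variances (400,000 trials per n) gave 94.5% at n = 31, 94.6% at n = 35 and 94.9% at n = 140.

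**Step 3: unequal variances.** With equal n the pooled and unpooled standard errors coincide, so the choice of estimator affects only the df. At n = 31, Welch's df lies between n − 1 = 30 and 2n − 2 = 60. At the lower bound t = 2.042, the interval is 4.2% wider than z, and z coverage is 94.1%. This is a bounding case. Variances may differ for the eight serotypes that are in SP0202 but not in Prevnar 13 (SAP section 1). Whether they do is unknown before data.

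**Step 4: the effect on reported limits.** This needs an SD, so a log10 SD of 0.3 to 0.6 is assumed. The limits are the ratio divided and multiplied by 10^(q × SD × √(2/n)), with q the quantile. At n = 31:

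| Assumed log10 SD | Multiplier, z | Multiplier, t | Lower limit at ratio 1, z | Lower limit at ratio 1, t |
|---|---|---|---|---|
| 0.3 | 1.410 | 1.420 | 0.709 | 0.704 |
| 0.4 | 1.582 | 1.597 | 0.632 | 0.626 |
| 0.5 | 1.774 | 1.795 | 0.564 | 0.557 |
| 0.6 | 1.989 | 2.018 | 0.503 | 0.496 |

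The lower limit moves by 0.005 to 0.007.

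**The case against.** The strongest reply is that the documents never say z or 1.96, and that the sponsor's own usage points away from it. The Protocol synopsis applies the phrase normal approximation to single-group CIs of quantitative data, and the SAP carries out those same CIs with Student's t. The SAP also attaches Student's t to the words about the usual calculation for a normal distribution. Read that way, the ratio phrase may mean normal theory on log10 values with a t quantile, and then nothing is too narrow.

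This stands. A reader might infer that every Stage I ratio interval is anti-conservative. The documents do not support that, because it holds only on the z reading.

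The second reply is that even under z the effect is immaterial: half a percentage point of coverage, in descriptive intervals with no margin, success criterion or power claim. Protocol section 12.1.1.2 offers between-group comparisons only for infants and only as optional, and the toddler ratios are an addition in the SAP. This stands too, and it limits the point to a minor improvement.

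Third, the 94.5% assumes exactly normal log10 data, whereas values below LLOQ are set to half the LLOQ and high values are capped at the ULOQ (SAP section 4.3.2.1). The figure is therefore conditional.

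None of these replies supplies the missing quantile, df or variance estimator.

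**Conclusion.** The point holds as an under-specified method with a small conditional effect. The SAP fixes the single-group interval fully but leaves the between-group ratio interval open.

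- **Under the literal z reading:** toddler ratio CIs at 31 per group are about 2% too narrow on the log10 scale, with about 94.5% coverage. This assumes normal log10 data and equal variances. The bounding case for unequal variances is 94.1%.
- **Under normal theory with a t quantile:** there is no shortfall.
- **In infants:** the difference is negligible on either reading.

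No planned test or margin depends on the choice. The case for changing the text is that a specified, correctly calibrated method is available at almost no cost and matches the SAP's own single-group method.

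**What to change.** In SAP section 5, below Table 5.1, replace the normal approximation for ratio CIs with a two-sample Student's t interval on log10 values, back-transformed. State the df and the variance estimator. Welch's interval with Satterthwaite df is a sensible choice where variances may differ, for example for the eight serotypes not in Prevnar 13.

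The Protocol synopsis and section 12.1.1.2 carry the same ratio wording. A line in SAP section 5.7 can record that the SAP now specifies the method.

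The cost is a short text edit and toddler intervals about 2% wider on the log10 scale than z would give (up to 4.2% in the bounding Welch case). Point estimates, sample size and analysis sets do not change. If the sponsor already intends a t quantile, only the wording changes.
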